4.2 Eligibility Criteria

4.2.1 **Inclusion Criteria**

Patients must meet all the following inclusion criteria to be eligible for enrollment into the study:

- 1) Signed informed consent approved by the Institutional Review Board (IRB). Patients must sign an authorization for the release of their protected health information;
- 2) Age ≥ 18 years;
- 3) Life expectancy > 12 weeks;
- 4) Present with histologically confirmed intracranial (supratentorial) unmethylated MGMT promotor status GBM (WHO Grade IV astrocytoma) with an MGMT status that has been confirmed by validated PCR or validated alternative genomic analysis;
- 5) Have undergone maximal or subtotal surgical resection of their tumor and within 6 weeks of surgery commenced radiation and then received at least 75% of planned treatment with XRT/TMZ or XRT only (if clinically indicated), which consists of XRT by external beam to a partial brain field in daily fractions of 2.0 Gray (Gy), to a planned total dose to the tumor of 60.0 Gy, in conjunction with TMZ oral QD 75 mg/m² in accordance with the Stupp regimen;
- 6) Karnofsky Performance Status (KPS) ≥ 70;
- 7) Cranial magnetic resonance imaging (MRI) must have been performed within 14 days prior to or on the day of the Enrollment/Week 1 Visit;
- 8) Stable or decreasing corticosteroid dose within 7 days prior to the first dose;
- 9) Adequate bone marrow/hematological function within 14 days prior to Day 1:
 - White blood cell count (WBC) > 3,000/µL, absolute neutrophil count > 1,500/mm³;
 - Platelet count of > 100,000/mm³;
 - Hemoglobin > 10 mg/dL;
 - Eligibility level for hemoglobin may be reached by transfusion;
- 10) Adequate liver function within 14 days prior to Day 1:
 - Total bilirubin ≤ 1.5 x ULN;
 - AST and ALT ≤ 2.5 x ULN;
- 11) Adequate renal function within 14 days prior to Enrollment/Week 1 Visit:
 - Creatinine ≤ 1.5 mg/dL;
 - Urine dipstick for proteinuria < 2+. Patients discovered to have ≥ 2+ proteinuria on dipstick urinalysis should undergo a 24-hour urine collection and must demonstrate ≤ 1.0 g of protein in 24 hours: OR
 - Urine protein/creatinine ratio ≤ 1.0;
- 12) International normalized ratio (INR) or prothrombin time (PT) (secs) and activated partial thromboplastin time (aPTT) within 7 days prior to Enrollment:
 - ≤1.5 x ULN (except for patients receiving anticoagulation therapy) in the absence of therapeutic intent to anti-coagulate the patient;

Version: Amendment 4 Date: 31 Mar 2020

- Within therapeutic limits (according to the medical standard in the institution) in the presence of therapeutic intent to anti-coagulate the patient;

 NOTE: Use of full-dose anti-coagulants is permitted as long as the INR or aPTT is within therapeutic limits (according to the medical standard in the institution) and the patient has been on a stable dose of anti-coagulants for at least 2 weeks before the Enrollment/Week 1 Visit. As per American Society of Oncology guidelines, low-molecular-weight heparin should be the preferred approach;

Protocol Number: NVGN-0084-201

IND Number: 112,608

- 13) Willing and able to comply with the protocol as judged by the Investigator:
- 14) Patients must be willing to forego other drug therapy against the tumor while enrolled in the study.

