- Grade ≥ 3 non-hematologic or non-hepatic toxicity that is not related to hyperglycemia or hyperlipidemia or mucositis/stomatitis and is not due to disease progression or another clearly identifiable cause, excluding the following:
 - Alopecia of any grade;
 - Grade 3 fever or Grade 4 fever < 5 days duration;
 - Grade 3 infection < 5 days duration or that responds to treatment;
 - Grade 3 weight gain or loss;
 - Grade 3 diarrhea lasting less than 5 days or that responds to standard-of-care therapy including hospitalization;
 - Grade 3 nausea or vomiting, in the absence of premedication, that lasts for less than 48 hours or responds to standard-of-care therapy:
 - Grade 3 or asymptomatic Grade 4 electrolyte imbalance that resolves or improves within 7 days with or without medical intervention, including hospitalization;
 - Grade 3 or 4 serum amylase or lipase or creatine phosphokinase laboratory abnormality that is asymptomatic (without other laboratory evidence suggestive of pancreatitis, rhabdomyolysis, or other major organ dysfunction) and returns to baseline within 7 days of interrupting study drug;

Version: Amendment 4 Date: 31 Mar 2020

Protocol Number: NVGN-0084-201 IND Number: 112.608

o Grade ≥ 3 total bilirubin or hepatic transaminase (aspartate aminotransferase [AST] and alanine aminotransferase [ALT]) elevations that return to ≤ Grade 1 (if normal at study entry) or ≤ baseline values within 7 days of interrupting study drug:

- Note: Allergic reactions that necessitate discontinuation of study drug will not be considered a DLT:
- Grade ≥ 3 symptomatic fasting hyperglycemia (e.g., dehydration or acidosis requiring hospitalization):
- Grade ≥ 4 fasting hypercholesterolemia or triglyceridemia for ≥ 14 days despite intervention with a lipid-lowering agent;
- Grade ≥ 4 thrombocytopenia;
- Grade 3 thrombocytopenia that lasts ≥ 7 days or is associated with clinically significant
- Grade ≥ 4 neutropenia (absolute neutrophil count < 500/µL) lasting ≥ 7 days or accompanied by fever (oral or tympanic temperature ≥ 38.0°C [100°F]);
- Grade ≥ 3 total bilirubin or hepatic transaminase (ALT or AST) elevations that do not return to ≤ Grade 1 (if normal at study entry) or ≤ baseline values within 7 days of interrupting study drug:
- For patients with Gilbert's disease and with Grade 2 bilirubin at baseline, total bilirubin ≥ 10 x upper limit of normal (ULN) will be considered a DLT;
- Bradycardia Grade ≥ 2;
- Myocardial ischemia Grade ≥ 2;

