4.10.5 Potential Hematological or Immunosuppressant Effects

As a result of observed changes in WBC count and absolute lymphocyte count in nonclinical toxicology studies with GDC-0084, patients will be required to have adequate hematologic function to enter the study and bone-marrow toxicities from prior therapies must be resolved before initiation of GDC-0084. Patients will be monitored routinely for changes in circulating blood cell counts, including a WBC count with differential. Because of the known immunosuppressive activity of mTOR inhibitors, patients who are immunocompromised as the result of human immunodeficiency virus will be excluded from the study. Many patients with high-grade gliomas will have received prior TMZ, a therapy that frequently causes lymphopenia. Such patients will be able to enroll in the trial and will be monitored closely for opportunistic infections. Prophylactic antibiotics such as sulfamethoxazole/trimethoprim are encouraged when the absolute lymphocyte count is < 500/µL. The decision to initiate prophylactic antibiotics should be discussed with the medical monitor.

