6.4 Sample Size

The sample size in Stage 1 is based on the 3 + 3 design. In Stage 2, no formal sample size calculation was performed. The number of patients planned to recruit is guided by practical rather than statistical considerations.

Stage 1 (dose-escalation) will enroll approximately 12 patients (range: 6 - 24 patients).

Stage 2 (dose expansion) will enroll 20 at the MTD established in Stage 1 for QD dosing.

The total sample size for this study is approximately 32 patients (range: 26 - 44 patients).

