8.2 Supply, Packaging and Labeling

The 15 mg GDC-0084 capsules will be produced and supplied by Kazia Therapeutics vendor(s) in accordance with GMP.

Primary packaging of the product will be 60CC white high-density polyethylene round bottle, induction sealed with child resistant closure. Each bottle contains 35 capsules.

Version: Amendment 4 Date: 31 Mar 2020

Protocol Number: NVGN-0084-201

IND Number: 112.608

Clinical labeling, warehousing and distribution, including returns, will be organized centrally. The label will contain the information as required by the relevant regulatory authority and national requirements. Labelling will be performed according to GMP and ICH GCP guidelines and local law.

Storage and Handling

The investigational product must be stored in securely locked areas not generally accessible until dispensed to the patients. The medication must be stored at between 15°C and 30°C (59°F-86°F).

The key to the storage area is to be kept by the Investigator or other person responsible for the medication. The store will be accessible only to those persons authorized by the Investigator to dispense study medication. The Investigator is responsible for the dispensing of medication according to the dosage regimen outlined in this protocol. All investigational product (partly used, unused and empty packaging) is to be left in the original packaging and must be returned to Kazia Therapeutics Limited's nominated vendor for destruction at the end of the study.

Accountability

The investigational product supplied by Kazia Therapeutics Limited is to be used exclusively in this clinical study according to the instructions of this protocol.

The Investigator must confirm the receipt of the investigational product with his/her signature. A copy of this receipt must be kept by the Investigator and another copy will be stored in the TMF. It is requested that any damaged or defective investigational product is promptly reported to the CRO and Kazia Therapeutics Limited.

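### The hemoglobin entry limit is printed in mg/dL, so as written it excludes nobody; as a minor second point, the two temperatures given for the neutropenic-fever DLT do not agree

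*Combined protocol and SAP*

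**What the plan says.** Criterion 9 asks for adequate bone marrow and hematological function within 14 days before Day 1. Its hemoglobin line reads "Hemoglobin > 10 mg/dL" in section 4.2.1, and item 9c of the synopsis uses the same figure and unit. The line after it adds "Eligibility level for hemoglobin may be reached by transfusion". Section 4.10.5 gives the purpose: "patients will be required to have adequate hematologic function to enter the study". The hemoglobin limit is not given in g/dL anywhere.

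Other provisions bear on anemia at entry:

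- Section 4.4.1 (Prior to Screening) requires side effects of chemoradiation to have recovered to baseline or Grade 1. Only lymphopenia and alopecia may be Grade 2.
- Section 4.10.5 requires bone-marrow toxicity from earlier therapy to have resolved before the study drug is started.
- Exclusions 7 and 16 in section 4.2.2 let the investigator exclude on clinical judgement; exclusion 16 expressly covers laboratory findings.

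On the second point, the definition of dose limiting toxicity (synopsis and section 3.7.1) counts Grade 4 or higher neutropenia if it lasts at least 7 days or comes with "fever (oral or tympanic temperature ≥ 38.0°C [100°F" (closing brackets omitted here). Both places print the same pair of temperatures.

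**The concern.** An entry criterion works only if some candidates can fail it. At 10 mg/dL nobody can, and a transfusion allowance for reaching that level has no use. Section 4.3 makes the investigator verify every criterion on an eligibility worksheet, so the printed limit is an instruction to sites and not background text. It is also the only hemoglobin figure in the protocol: the retreatment criteria (section 4.9.1) list neutrophils, platelets, bilirubin and transaminases, and the hematologic DLTs cover thrombocytopenia and neutropenia. In addition, section 6.3.1 defines the mITT, safety and PK populations on eligible patients, so a patient's eligibility status carries through to the analysis sets.

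The fever pair matters because it lies inside the primary endpoint (section 4.5.1). Under the 3 + 3 rules in section 3.7.1, a first DLT among three patients turns escalation into expansion of the cohort, and a second fixes the MTD one level lower. A threshold with two values leaves such a call open.

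**Working it through.** **Hemoglobin**

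Input: limit of 10 mg/dL (synopsis item 9c; section 4.2.1, criterion 9). Conversion: 1 g = 1000 mg.

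- Printed limit in g/dL: 10 / 1000 = 0.01 g/dL.
- The same number read in g/dL: 10 × 1000 = 10,000 mg/dL.
- Ratio of the two readings: 10,000 / 10 = 1000.

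The hemoglobin values below are assumed for illustration and are not from the protocol. The last column uses the presumed unit.

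| Hemoglobin (g/dL) | In mg/dL | Passes > 10 mg/dL | Passes > 10 g/dL |
|---|---|---|---|
| 2 | 2,000 | yes | no |
| 6 | 6,000 | yes | no |
| 8 | 8,000 | yes | no |
| 10 | 10,000 | yes | no |
| 12 | 12,000 | yes | yes |
| 15 | 15,000 | yes | yes |

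Every value passes as printed.

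**What the other entry rules still cover**

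- Anemia caused by chemoradiation and above both baseline and Grade 1: section 4.4.1 bars entry, since anemia is not among its Grade 2 exceptions. Section 4.10.5 points the same way.
- Anemia the investigator considers clinically important: exclusions 7 and 16 allow exclusion, by judgement and without a number.
- Anemia not caused by prior therapy, or already present at baseline: no hemoglobin figure applies.

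**Fever**

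Inputs: 38.0°C and 100°F (synopsis; section 3.7.1). Formula: °F = °C × 9/5 + 32.

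- 38.0 × 9/5 + 32 = 100.4°F. The printed 100°F is reproduced only by rounding to a whole degree.
- (100 − 32) × 5/9 = 37.8°C.
- Gap: 100.4 − 100.0 = 0.4°F, or 0.4 × 5/9 = 0.2°C.

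The storage instruction in section 8 provides a comparison: "The medication must be stored at between 15°C and 30°C (59°F-86°F". There 15 × 9/5 + 32 = 59 and 30 × 9/5 + 32 = 86, so that pair converts exactly.

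A reading from 100.0 to just under 100.4°F meets the Fahrenheit figure and not the Celsius one. It decides the DLT call only if the Grade 4 neutropenia lasts under 7 days, because longer neutropenia is a DLT without fever. The event must also fall in Cycle 1 and be judged possibly or probably related, and the patient must have no other DLT.

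**The case against.** The strongest reply is that little follows in practice. Most sites would probably read the hemoglobin limit as g/dL, and nothing here touches a sample size, an error rate or an analysis method; for Stage 2 the protocol says "In Stage 2, no formal sample size calculation was performed". That stands, and it makes this a wording error in an operative threshold and not a design flaw. It does not remove the need for correction, because it relies on each site silently amending the protocol.

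A reader might infer from the printed unit that the protocol sets no limit on anemia after chemoradiation, and that a severely anemic patient could enter with no deviation to record. The documents do not support this. Enrolling a patient whose treatment-related anemia had not recovered as section 4.4.1 requires would breach that section, and section 4.10.5 and exclusions 7 and 16 restrict entry further.

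A reader might also treat the fever pair as an error of the same kind. It is not: the gap is 0.4°F and fits whole-degree rounding of the Celsius figure. Nor does one such reading by itself change the escalation decision. It can do so only when the conditions listed above coincide, and a first DLT expands the cohort without ending escalation. DLTs are assessed by the sponsor with the investigators at Cohort Review Committee meetings (sections 3.7.1 and 7.1), which limits differences between sites. What remains is that the Celsius figure carries a decimal, the pair defines a cut-off, and the two cut-offs differ.

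**Conclusion.** The concern holds in a limited form. As printed, the hemoglobin line of criterion 9 is 0.01 g/dL and excludes nobody, against the evident intent of the transfusion allowance and section 4.10.5. The factor of 1000 rests on the assumption that g/dL was meant, inferred from the usual reporting unit; only the sponsor can confirm it. Because synopsis and body agree, a one-off text-extraction fault is unlikely. The gap left by the other entry rules is the lack of a working numeric limit, chiefly for anemia that is not treatment-related or that was present at baseline.

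The fever mismatch is real but minor: a band of 0.4°F (0.2°C) in which a DLT call can go either way. How often it would arise cannot be estimated from the documents. Section 4.1 places all sites in the US, but recording in Fahrenheit is an assumption. No view is taken on which temperature is right.

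Both items should be corrected, since each is a decision threshold.

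**What to change.** 1. The sponsor should confirm the intended hemoglobin unit (presumably g/dL) and correct synopsis item 9c and section 4.2.1 criterion 9 together.
2. Check that the eligibility worksheet named in section 4.3 uses the same unit. The worksheet is not among the documents, so whether it carries the error is unknown.
3. In the DLT definition, in both the synopsis and section 3.7.1, reconcile the Celsius and Fahrenheit figures to a single temperature, or give only one scale.

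The cost is four one-word or one-number corrections at the next amendment and one check of the worksheet. The design and analyses are unchanged.

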4.2.2 Exclusion Criteria

Patients presenting with any of the following will not be included in the study:

- 1) Previous radiotherapy to the brain or cytotoxic drug therapy (including Gliadel® wafers) in addition to the required postoperative radiation plus TMZ, non-cytotoxic drug therapy, or experimental drug therapy directed against the brain tumor prior to this regimen, will be excluded. Patients may have received or be receiving corticosteroids, analgesics, and other drugs to treat symptoms or prevent complications but the dose must be stable at treatment start. NOTE: 5 aminolevulinic acid-mediated photodynamic therapy administered prior to surgery to aid in optimal surgical resection is not considered a chemotherapy agent;
- 2) Any prior, or anticipated, concomitant treatment involving a medical device (such as Optune®) applying tumor treating fields (TTF). Prior short-course Optune® monotherapy (i.e. without concurrent TMZ or other chemoRx) may be allowed with approval from the Medical Monitor
- 3) QT interval time of ≥ 470 msec;
- 4) Undetermined/indeterminate MGMT status;
- 5) Diabetic patients and/or ongoing use of insulin therapy; clinically confirmed prediabetic patients;
- Use of any strong CYP3A4 inducing or inhibiting agents within 14 days of first dose of GDC-0084;
- 7) Significant medical illnesses that in the Investigator's opinion cannot be adequately controlled or would compromise the patient's ability to tolerate this therapy;
- 8) Women who are pregnant (determined by serum beta chorion-gonadotropin) or who are lactating. NOTE: Serum pregnancy test to be assessed within 7 days prior to first dose;
- 9) Any disease likely to obscure toxicity;
- 10) Diagnosed with infratentorial GBM;
- 11) Diagnosed with tumor outside of brain;
- 12) Diagnosed with gliomatosis cerebri;
- 13) Evidence of recent hemorrhage on postoperative MRI of the brain. However, patients with clinically asymptomatic presence of hemosiderin, resolving hemorrhagic changes related to surgery, and presence of punctate hemorrhage in the tumor are permitted entry into the study;
- 14) Male and female patients of childbearing potential unwilling or unable to use effective means of contraception (oral contraceptives, intrauterine contraceptive device, barrier method of contraception in conjunction with spermicidal jelly) throughout the study and for at least 28 days after the last dose of assigned treatment;
- 15) Any previous malignancy; except for adequately controlled limited basal cell carcinoma of the skin, squamous carcinoma of the skin or carcinoma *in situ* of the cervix, or any previous malignancy which has been absent of evidence of disease and has not required treatment for ≥ 3 years;

Date: 31 Mar 2020

Protocol Number: NVGN-0084-201 Version: Amendment 4 IND Number: 112,608

16) Patients who have any other disease that would in the judgement of the investigator, exclude enrollment in this study. Disease could be either metabolic or psychological, and based upon any evidence on clinical examination or special investigations (including a laboratory finding);

- 17) Any other investigational drug or participation in another investigational study within 30 days prior to Enrollment/Week 1;
- 18) Known hypersensitivity to any excipients of GDC-0084 formulation or of other PI3K/mTOR inhibitors;
- 19) Unable to comply with the administration of the study treatment.

4.2.3 **Contraception Guidelines**

All male and female patients who, in the opinion of the Investigator, are biologically capable of having children and are sexually active, must agree to use a highly effective method of contraception consistently and correctly for the duration of the active treatment period and for at least 30days after the last dose of investigational product. The Investigator, in consultation with the patient, will select the most appropriate method of contraception for the individual patient from the permitted list of contraception methods, and instruct the patient in its consistent and correct use. The Investigator, at each study visit, will confirm and document consistent and correct use. In addition, the Investigator will instruct the patient to call immediately if the selected birth control method is discontinued or if pregnancy is known or suspected.

Highly effective methods of contraception are those that, alone or in combination, result in a failure rate of less than 1% per year when used consistently and correctly and include:

- Established use of oral, injected or implanted hormonal methods of contraception;
- Correctly placed intrauterine device or intrauterine system;
- Male condom or female condom used TOGETHER WITH a spermicide (i.e., foam, gel, film, cream, suppository);
- Male sterilization with appropriately confirmed absence of sperm in the post-vasectomy eiaculate:
- Bilateral tubal ligation or bilateral salpingectomy.

